10 STATISTICAL ANALYSIS AND DATA MANAGEMENT

10.1 STATISTICAL ANALYSIS

All data will be analyzed by CORE at the University of Waterloo. Data analysis will be conducted using Statistica, SPSS, or other appropriate software.

Descriptive statistics will be provided for all primary outcome variables as well as information regarding baseline variables (e.g. age, sex).

Subjective ratings, lens fit assessments and time to haze will be compared between Visit 2 (Precision1 Dispense) and Visit 3 (2-week follow-up) using either Paired t-tests or Wilcoxon matched pairs, or using ANOVA, as applicable; statistical significance will be set at 5%. The appropriate tests will be selected based on tests of normality - non-parametric tests will be used for data not showing a normal distribution. For assessments conducted for each eye separately, the right eye will be used for analysis if there is no difference between eyes.

Binomial testing will be conducted to analyze Likert questionnaires (strongly agree, slightly agree, slightly disagree, strongly disagree) to determine whether participants had a positive or negative experience with the test lens.

Additional analysis may be conducted.

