4.2 STUDY POPULATION

4.2.1 SAMPLE SIZE CALCULATION

The sample size required for a 2-tailed matched paired t-test to detect a change of 5 points in a 0-100 subjective rating scale, with $\alpha=0.05$, power = 0.90, and an effect size of 0.60 is 32 to complete the study, i.e. a minimum sample size of 32 participants completing the study.

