4.2.2 NUMBER OF PARTICIPANTS

Participants will be recruited / screened using CORE records and advertising approved by the UW Office of Research Ethics. Up to 35 participants who meet all eligibility criteria may be dispensed with Precision1 study lenses and asked to wear these lenses for 14 ± 2 days, with a target of 32 completing the study. Participants who were screened but did not meet all eligibility criteria are not included in the number of participants (n=35) to be dispensed. Informed consent will be obtained for all participants prior to their enrolment in the study (Appendix 1).

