4.5.7 LENS FIT & SURFACE ASSESSMENT

Contact lens fit:

Lens fit will be assessed to ensure acceptable lens fit with study lenses at the screening visit.

At V2 and V3, lens centration and movement will be assessed as follows

- *Lens centration (scale: optimal, slight decentration, moderate decentration but not encroaching limbus, excessive & occasionally encroaching limbus);*
- *Lens movement for primary gaze (-2 = Unacceptably tight; -1 = Slightly tight but acceptable; 0 = Optimal; +1 = Slightly loose but acceptable; +2 = Unacceptably loose); lens tightness on push-up test (0-100 scale, with 50 being optimal; 5-point steps);*

Contact lens wettability, pre-lens tear break-up time and deposits:

Contact lens wettability and deposits will be graded with study lenses at V2 and V3:

- *Surface wettability (0-4 scale in 0.25 steps; 0 being excellent);*
- *Pre-lens tear break up time (TBUT), average of 3 measures (seconds)*
- *Surface deposits (0-4 scale in 0.25 steps; 0 being excellent);*

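### The right-eye rule in section 10.1 rests on an undefined between-eye condition, has no analysis for the other branch, and gives up modest precision on secondary outcomes

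*Combined protocol and SAP*

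**What the plan says.** Section 10.1 has one sentence on per-eye data. For assessments made in each eye, "the right eye will be used for analysis if there is no difference between eyes". It adds no definition of a difference and no instruction for the case where one is found.

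The same section plans these comparisons: "Subjective ratings, lens fit assessments and time to haze will be compared between Visit 2 (Precision1 Dispense) and Visit 3 (2-week follow-up"). The tests named are the paired t-test, the Wilcoxon matched-pairs test and ANOVA, at a 5% level. No eye average and no model with eye within participant is mentioned. Lens fit is named among the compared outcomes; the surface measures are not named separately.

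Section 4.5.7 lists three fit grades (centration, primary-gaze movement, push-up tightness) and three surface measures (wettability, pre-lens tear break-up time, deposits). On timing it says: "Contact lens wettability and deposits will be graded with study lenses at V2 and V3". It does not say whether these are recorded for each eye. Section 4.3.1 has the lenses worn in both eyes, so per-eye recording is likely, but it is an inference. Study-lens acuity is explicitly recorded for the right eye, the left eye and both (section 4.4.4).

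**The concern.** The rule has three weaknesses.

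- **The condition is undefined.** Section 10.1 does not say which test or threshold applies, at which visit, on values or on change, or whether the decision is made outcome by outcome or once for all. Whether the left eye enters the analysis is therefore decided after the data are seen.
- **One branch is missing.** If the eyes are judged to differ, nothing says whether the right eye, the left eye, both or an average is analysed. The allowances for ANOVA where applicable and for additional analyses do not fill that gap.
- **Precision is given up where it need not be.** If the eyes behave alike, their mean estimates the same change with a smaller standard error.

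At stake are the width of the intervals for fit and surface changes and the freedom to choose the analysed eye once results are known.

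**Working it through.** **1. The plan's own figure.** Section 4.2.1 sizes the study for a "2-tailed matched paired t-test to detect a change of 5 points in a 0-100 subjective rating scale" and states "power = 0.90, and an effect size of 0.60 is 32 to complete the study". Using the noncentral t with n − 1 degrees of freedom and noncentrality 0.60 × sqrt(n), power is 0.898 at n = 31 and 0.908 at n = 32. The figure of 32 reproduces. The implied SD of the change is 5/0.60 = 8.33 points.

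**2. What the rule touches.** The ratings behind that calculation are one score for both eyes together (sections 4.4.3, 4.4.4 and 4.5.2), so the right-eye rule does not reach them. It reaches only outcomes that section 2 lists as other outcomes of interest.

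**3. Precision of one eye against two.** Let r be the between-eye correlation of the Visit 3 minus Visit 2 change, with equal variance in each eye. Then

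Var(two-eye mean) / Var(one eye) = (1 + r)/2

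SE ratio = sqrt((1 + r)/2)

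Equivalent n = 32 / ((1 + r)/2)

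The documents give no r, so a range is assumed.

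| r (assumed) | SE ratio | SE reduction | Equivalent n | Extra participants |
|---|---|---|---|---|
| 0.5 | sqrt(0.75) = 0.866 | 13.4% | 32/0.75 = 42.7 | 10.7 |
| 0.8 | sqrt(0.90) = 0.949 | 5.1% | 32/0.90 = 35.6 | 3.6 |
| 0.9 | sqrt(0.95) = 0.975 | 2.5% | 32/0.95 = 33.7 | 1.7 |

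Seen from the other side, the right-eye confidence interval is 15.5%, 5.4% or 2.6% wider than the two-eye interval. As an illustration only, suppose the right-eye change had a standardised effect of 0.60. Power at n = 32 would rise from 0.908 to 0.967, 0.934 or 0.921.

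**4. What a non-significant between-eye result shows.** Suppose the condition were a paired 5% test on 32 participants; the plan does not say so. The SD of the between-eye difference is sqrt(2(1 − r)) one-eye SDs, where r is now the correlation of whatever quantity is compared. For a true difference of 0.3 SD the standardised effect is 0.3/sqrt(2(1 − r)):

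- r = 0.5: 0.300, power 0.38
- r = 0.7: 0.387, power 0.57
- r = 0.8: 0.474, power 0.74
- r = 0.9: 0.671, power 0.96

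Except at very high correlation, failing to find a difference of this size would be weak evidence that the eyes agree.

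**5. The wrong way to use both eyes.** Entering 64 eye records from 32 participants as independent values gave a simulated type I error of 11%, 15% and 16% at r = 0.5, 0.8 and 0.9, against a nominal 5%. The gain in step 3 comes only from an analysis that keeps the participant as the unit.

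**The case against.** The strongest reply is that analysing one eye is a recognised and valid choice. It respects the correlation within a person and does not bias the visit comparison for that eye. The outcomes concerned are secondary, in a study that section 4.1.1 calls a pilot. Fixing the right eye unconditionally would close the logical gap without any averaging. All of this stands, and it keeps the point minor. It does not rescue the sentence as written, because section 10.1 makes the right eye conditional.

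Four stronger readings are tempting, and the documents do not support them.

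- A reader might infer that half the information is discarded. Half the records go unused, but the loss in equivalent sample size is about 25%, 10% or 5% at r = 0.5, 0.8 or 0.9. It would be half only at r = 0.
- A reader might infer that the primary result or the planned 32 completers is undermined. Both rest on ratings of the two eyes together.
- A reader might infer a 26% chance of reaching the unspecified branch by accident, from 1 − 0.95^6 over the six fit and surface measures. That needs six independent 5% tests between eyes. Section 10.1 does not say that the condition is tested in this way; its 5% level is attached to the visit comparison.
- A reader might infer that averaging the eyes is a safe remedy for every measure. Push-up tightness is optimal at 50, so eyes at 30 and 70 would average to 50 and hide two opposite misfits. Centration and primary-gaze movement are ordered categories that a simple mean does not suit. Study-lens acuity has no Visit 2 value, since Table 3 places it at Visits 1 and 3.

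**Conclusion.** The point holds, with minor severity. The firmer defect is one of specification: an undefined, data-dependent condition with no stated analysis on its other side. The efficiency loss is secondary. It amounts to a standard error about 2.5% to 13% larger than a two-eye mean would give (taking the two-eye gain as the measure), or about 2 to 11 participants at n = 32, for r from 0.9 down to 0.5.

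These sizes assume equal variances in the two eyes, the stated range of r, and per-eye recording of fit and surface, which section 4.5.7 does not confirm. They also assume that the surface measures are compared between visits, although section 10.1 names only lens fit. None of these assumptions is needed for the specification gap, which can be read directly from the sentence.

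**What to change.** Delete the between-eye condition from section 10.1, list the outcomes recorded per eye, and state one unconditional rule for the Visit 2 versus Visit 3 comparisons:

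- **Wettability, pre-lens tear break-up time and deposits**, where compared: the participant-level mean of the two eyes.
- **Push-up tightness**: a model with eye nested in participant, or an analysis of each eye's distance from the optimum of 50. Using that distance as the response is preferable, because the mean from a model of the raw score would still let opposite deviations offset each other.
- **Centration and primary-gaze movement**: an ordinal model clustered by participant, or the right eye fixed in advance.
- **All per-eye outcomes**: both eyes tabulated descriptively, and the two eyes never treated as independent observations.

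Leave acuity out of this wording, because it is measured with the study lens at Visits 1 and 3. If the team prefers the simplest route, naming the right eye unconditionally for every per-eye outcome would cure the specification gap, at the precision cost shown above.

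The cost is a few sentences and slightly more analysis work. No visit or participant is added, and no measurement either if both eyes are already graded, as bilateral wear suggests. The sample size stays at 32 completers.

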10.2 DATA MANAGEMENT

All study data will be recorded on paper CRFs. Data from this study will be entered in an electronic database and retained by CORE for a minimum of 25 years on a password-protected server. After 25 years, data will be disposed of in accordance with the guidelines laid out by the University of Waterloo.

At the completion of the study CORE may provide a copy of the study data to the funding company. Data will typically be sent using a secure file share system operated by the University of Waterloo called Sendit which uses 128bit (or 256bit) SSL encryption. This system provides a secure way to transfer files when email is not appropriate, whether because of file size, file type

or concerns over security. Sendit includes features such as password protection, a restricted time period for download, IP logging and email notification of download. Files may be encrypted prior to transmission. Using this method means that data files are only stored on University of Waterloo servers during the transfer.

10.3 COMMENTS ON SOURCE DOCUMENTS

Data analysis will not be conducted on comments which have been recorded in the source documents. Only relevant and applicable comments will be included in the final report as deemed necessary by the lead investigator.

11 PROTOCOL TRAINING

All study personnel will be required to complete training prior to their involvement in the study. Records of training will be kept at CORE.

12 STUDY MONITORING

Study monitoring will be conducted throughout the study. In addition study records may be inspected at CORE by the Office of Research Ethics at the University of Waterloo, and by regulatory authorities in Canada and the United States, namely Health Canada and the United States Food and Drug Administration (FDA); however, no records containing identifiable/personal information will be permitted to leave the custody of CORE.

Study monitoring will include, but may not be limited to:

- The number of participants screened, enrolled, and randomized (i.e. assigned a study ID number), discontinued and completed;
- Consent documentation;
- Details of adverse events and protocol deviations;
- Reports of unintended events.

13 STUDY MANAGEMENT

13.1 STATEMENT OF COMPLIANCE

This clinical study is designed to be in compliance with the ethical principles in the Declaration of Helsinki, with the ICH guidelines for Good Clinical Practice (GCP), with the University of

Waterloo's Guidelines for Research with Human Participants and with the Tri-Council Policy Statement: Ethical Conduct for Research Involving Humans, 2nd Edition.

- Declaration of Helsinki
- ICH E6 - International Conference on Harmonisation; Good Clinical Practice
- <http://iris.uwaterloo.ca/ethics/human/guidelines/index.htm>
- <http://iris.uwaterloo.ca/ethics/human/ethicsReview/UWStatement.htm>
- <http://www.pre.ethics.gc.ca/eng/policy-politique/initiatives/tcps2-eptc2/Default/>

13.2 ETHICS REVIEW

This protocol will be submitted to and reviewed through the Office of Research Ethics (ORE) at the University of Waterloo. Notification of ethics clearance of the application is required prior to the commencement of the study.

13.3 CLINICAL TRIAL REGISTRATION

CORE will register this study with clinicaltrials.gov.

13.4 PROTOCOL DEVIATIONS

Protocol deviations are unanticipated or unintentional changes to a study after it has received prior sponsor approval and ethics clearance. Protocol deviations can be major or minor.

13.4.1 MAJOR PROTOCOL DEVIATIONS

Major protocol deviations may impact the research protocol, information consent document or other study materials, usually cannot be anticipated ahead of time and are often necessary to ensure the safety and welfare of the participants.

The following are examples of protocol deviations that must be reported to the ORE:

- Changes in procedures initiated to eliminate immediate risks/hazards to participants;
- Enrollment of participants outside the protocol inclusion/exclusion criteria whether agreed to or not by the sponsor;
- Medication / device / intervention errors (i.e. incorrect drug or dosage of drug / incorrect contact lens(es) dispensed / incorrect care system dispensed);
- Inadvertent deviation in specific research intervention procedures or timing of the research intervention which could impact upon the safety or efficacy of the study-related intervention or upon the experimental design;

- Information consent documentation violations: no documentation of informed consent; incorrect version of, or incomplete, informed consent documentation used.

13.4.2 MINOR PROTOCOL DEVIATIONS

Protocol deviations caused by or which originate with research participants are considered minor, and normally are not reported to the ORE unless these result in increased risk to the participant(s). The following are examples of protocol deviations that are considered minor and do not require reporting to the ORE:

- Logistical or administrative aspects of the study (e.g., study participant missed appointment, change in appointment date);
- Inadvertent deviation in specific research intervention procedures or timing of the research intervention which would not impact upon the safety or efficacy of the study-related intervention or upon the experimental design (i.e., missing a measurement during a session that is not considered critical for the study).

13.4.3 REPORTING AND DOCUMENTING PROTOCOL DEVIATIONS

Major protocol deviations must be reported to the ORE within 7 days of the deviation occurring (or its discovery) using the Protocol Deviation Report Form 107 (PDRF). Information from the PDRF is provided to the Clinical Research Ethics Committee (CREC) at the next monthly meeting.

All protocol deviations (major and minor) occurring during the study will be documented and included in the final report.

13.5 PREMATURE TERMINATION OF THE STUDY

The sponsor, CORE or the Office of Research Ethics at the University of Waterloo may terminate the study at any time for any reason.

13.6 STUDY PARTICIPANT RECORDS

Study participant records will be completed to comply with GCP guidelines. Records will contain:

- Unique study acronym and/or code;
- Participant ID;
- Date enrolled;
- Confirmation by investigator that participant met eligibility criteria;

- Confirmation that participant received a signed and dated copy of informed consent;
- Exit date;
- Investigator's signature confirming study exit.

13.7 RETENTION OF STUDY RECORDS AND DATA

Records and data from this study will be retained for a minimum of 25 years. Details regarding storage procedures are given in CORE SOP014_v02 Clinical data management.

14 REPORT

A report will be completed after data collection has been completed.

